women and the same 10 HCPs from Aim 1 to evaluate the #HerHeart tool's usability and feasibility. AYA participants will complete a brief initial survey consisting of demographic information and the Visual Analog Scale (VAS) and the #HerHeart tool in clinic. AYA participants will the rate the usability of the #HerHeart tool using the Website Analysis and Measurement Inventory (WAMMI), the likelihood they would recommend the app to their friends, and the likelihood of behavior change. AYA participants will then be offered the opportunity to continue into the 3-month intervention phase. We will document the reasons for declining as part of tracking feasibility. At the beginning of the intervention phase, participants will complete the Eating Disorder Diagnostic Scale (EDDS). Participants will then be texted 1 month and 2-months post-enrollment reminding them of any goals/areas of improvement indicated by their end assessment in the #HerHeart Tool. Three months post-enrollment, participants will attend the final study visit in the phlebotomy room on the second floor of CHOA Hughes Spalding. In this visit, AYA participants height, weight and blood pressure will be measured. Participants will also be asked to complete the #HerHeart tool again and the same online study scales collected at baseline (EDDS and VAS). They will also be asked to complete the Harvard Healthy Heart Score and evaluate the usability using the WAMMI. HCP participants will complete a survey consisting primarily of demographic information and the #HerHeart tool. HCP participants will then rate the usability of the tool using the WAMMI, the usefulness of the #HerHeart to their practice and the likelihood they would incorporate it into usual clinical care.

Data analysis will consist of descriptive statistics for the WAMMI and Likert scale surveys. Usability will be defined as >80% of AYA and HCP rating the application as above average on the WAMMI. Acceptability to HCP will be defined as a mean of 8 out of 10 Likert Scale items. Paired t-tests will be used to compare the baseline and 3-month data for the continuous scales (EDDS, VAS).

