Primary outcomes will include changes in overall #HerHeart risk score, composite dietary score, fruit and vegetable intake, red/processed meats intake, soda and sweetened beverages intake, nut consumption, cereal fiber consumption, alcohol consumption, nicotine use, and physical activity over a 3-month period. Secondary outcomes will include changes in BMI and systolic and diastolic blood pressure over a 3-month period. Exploratory outcomes will include usability of the HerHeart tool and Healthy Heart Score as assessed by the WAMMI, adolescents' likelihood of recommending the tool to friend, adolescents' self-reported likelihood of behavior change, adolescents' understanding of heart disease risk as measured by VAS, change in EDDS score, number of participants approached and participated, completion/dropout rate, HCP rated usefulness of HerHeart tool to the practice, and HCP rated likelihood of

incorporating HerHeart tool into practice.

All phases: The probability and magnitude of risks will be minimized by conducting study procedures in private settings, collecting data in REDCap, a secure web-based application designed exclusively to support data capture for research studies, and collaborating with the Georgia CTSA to ensure data security of the mobile app.

6. Data and Specimen Banking

Data from surveys/questionnaires, audio recordings, and interviews will be stored until the completion of data analysis and manuscript publication. Only approved study personnel listed on the protocol will have access to the data.

7. Sharing of Results with Participants

Personal Healthy Heart Score risk assessments will be shared with participants at each stage of the study. Participants will be encouraged to share their results with their primary care physicians, but results will not be directly shared with others.

8. Study Timelines

Individuals in Aim 1/Phase 1 will participate for ~one hour, one time. Individuals in Aim 2/Phase 2 will participate for up to two hours for each design session which will occur over 6 months. Aim 3/phase 3 will occur over 3 months. The total duration of the overall study is 15 months, which includes subject participation and data analysis.

9. Subject Population

Subjects will be recruited from the CHOA Hughes Spalding Adolescent Medicine Clinic and the Grady Teen Health Program. The following inclusion/exclusion criteria will be used for subject recruitment:

Inclusion Criteria (AYAs):

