the study procedures as described in Section 6. Consent and study procedures will only occur in the context of a study visit, and not via initial phone screening and recruitment.

To assist with recruitment efforts, a recruitment flyer containing information about the study (eligibility requirements, study procedures, time commitment, etc.) will be distributed in the CHOA Adolescent Medicine practice. The flyers will be distributed to eligible patients who may not have time to begin the study procedures due to normal clinic flow (i.e., patient gets called back to exam room before we can consent them and begin the study).

Compensation for participants will be as follows:

- Aim 1: AYA and HCP subjects will receive a \$25 gift card.
- Aim 2: AYA subjects will receive a \$50 gift card.
- Aim 3: AYA will receive up to \$60 and HCPs will receive \$25

13. Withdrawal of Participants

Participants will be told that they can drop out of the study at any time during the study. Participants who become pregnant or become cognitively impaired throughout study duration will be withdrawn from the study without their consent. Furthermore, participants who become otherwise unable to participate in the research procedures due to health-related concerns will be withdrawn from the research without their consent at the discretion of the PI. Data collection will cease for participants who withdraw from the research and these individuals will not be included in the final data analysis.

14. Risks to Participants

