This proposed study involves no more than minimal risk. Completion of the Healthy Heart risk assessment tool in its current form includes the risk that AYA participants disclose heavy alcohol or tobacco use. Participants may find learning about their cardiovascular risk distressing. After learning about their cardiovascular risk, participants may make changes to their exercise or dietary habits outside of what is recommended in the behavioral intervention or would be recommended by their HCP. Participation in the interviews also carries the risk of AYA's self-disclosure of health information. All efforts will be made to remind participants not to provide identifying information during the interviews. Breach of confidentiality is a risk for both AYA and HCP participants. To ensure participant confidentiality, study identification numbers will be assigned to each participant and used throughout the duration of the study when referring to subjects. The codes that link the name of the participant and the study identification number will be kept confidential by the PI in a secured cabinet. Only the authorized study team with appropriate training will have access to the data.

The direct benefit to AYA participants in the survey and interviews in each aim is gaining information about their health. The direct benefits to HCP in Aim 1 includes learning about new tools or methods that can potentially be used to increase CVD awareness in patients. Overall this study has the potential to inform prevention practices applicable to millions of young women living in the United States and to possibly lower the burden of cardiovascular disease among women.

Though not considered a benefit, subjects will be compensated for participation in this study. In Aim 1, AYA and HCP subjects will receive a \$25 gift card for completing surveys and interviews. In Aim 2, AYA participants will receive a \$50 gift card for participating in the design sessions. In Aim 3, AYA participants will receive \$25 for completing the usability assessment and up to \$35 for completing the intervention phase; HCPs will receive \$25 for completing the usability assessment.

16. Data Analysis, Management and Confidentiality

The main aim of the proposed study is to adapt the Healthy Heart Score tool based on participant feedback. As such, all data will be descriptive only.

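### As written, the Section 13 withdrawal rule drops Phase 3 usability ratings given before withdrawal; any resulting bias is of unknown size and direction

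*Combined protocol and SAP*

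**What the plan says.** Section 13 (Withdrawal of Participants) sets one rule for the whole study: "Data collection will cease for participants who withdraw from the research and these individuals will not be included in the final data analysis". It names no phase, outcome or time point, and makes no exception for data already in hand. The same section allows drop-out at any time. It also has the study withdraw participants for pregnancy, cognitive impairment or other health reasons.

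Section 5 (Phase 3 procedures) has AYA participants complete #HerHeart, rate it on the WAMMI, and rate how likely they are to recommend it and to change their behaviour. Only after that: "AYA participants will then be offered the opportunity to continue into the 3-month intervention phase". Of those who say no, it states: "We will document the reasons for declining as part of tracking feasibility". The compensation paragraph under Section 14 treats the two steps separately, paying AYA participants $25 "for completing the usability assessment and up to" $35 for the intervention phase.

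The usability criterion in Section 5 is: "Usability will be defined as >80% of AYA and HCP rating the application as above average on the WAMMI". It is not tied to an analysis set. Section 4 makes usability part of the Phase 3 primary endpoint, whereas Section 5 says: "Exploratory outcomes will include usability of the HerHeart tool and Healthy Heart Score as assessed by the WAMMI". The same exploratory list includes "number of participants approached and participated, completion/dropout rate". Section 16 adds: "As such, all data will be descriptive only".

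**The concern.** Stopping new data collection at withdrawal is normal. Removing the person from the analysis altogether is a different step, and here it reaches data that were complete before the withdrawal. The #HerHeart WAMMI and the two likelihood ratings are given once, at the first session, and nothing that happens during the following three months makes them invalid.

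Two things are at stake. Valid ratings are lost from a sample of only about 60 AYA raters. The usability percentage may also be selected on staying in the study: too high if withdrawers liked the tool less, too low if they liked it more, and unchanged if they rated it the same. Voluntary drop-outs might plausibly like the tool less, but withdrawal for pregnancy or health need not be related to the rating.

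The other 3-month outcomes are not affected in this way. Change scores and the WAMMI for the Healthy Heart Score need the final visit, so a withdrawer could not contribute to them in any case.

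**Working it through.** The plan gives no withdrawal rate, power or sample-size calculation, so there is no stated figure to reproduce. The check is exact counting on the >80% rule.

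**Inputs**
- Phase 3 AYA raters: N = 60 (Section 2, Aim 3). All are assumed to complete the baseline WAMMI.
- Criterion: more than 80% above average (Section 5). The table uses AYA only; the pooled reading follows it.
- Withdrawals after rating: w = 3, 6 or 12. **These counts are assumed.**
- Gap between stayers and withdrawers in the proportion favourable: 15 or 35 points (assumed).

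**Passing count with all ratings kept.** 48/60 = 80.0% is not above 80%, so at least 49/60 = 81.7% is needed.

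**Shift in the reported percentage.** Shift = (w/60) × (p_stay − p_withdraw). The sign reverses if withdrawers rate higher.
- w = 3: 0.05 × 15 = 0.75 points; 0.05 × 35 = 1.75 points
- w = 6: 0.10 × 15 = 1.5 points; 0.10 × 35 = 3.5 points
- w = 12: 0.20 × 15 = 3.0 points; 0.20 × 35 = 7.0 points

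**When the pass or fail result changes, w = 6 (54 stayers).** Let k be the number of the 6 withdrawers who were favourable. The all-rater result passes if stayers' favourable count + k ≥ 49.

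| Favourable stayers | Reported | All 60 raters differ if | Gap at that boundary |
|---|---|---|---|
| 43/54 | 79.6%, fail | k = 6 (49/60 = 81.7%, pass) | −20.4 points |
| 44/54 | 81.5%, pass | k ≤ 4 (at most 48/60, fail) | 14.8 points |
| 45/54 | 83.3%, pass | k ≤ 3 | 33.3 points |
| 46/54 | 85.2%, pass | k ≤ 2 | 51.9 points |
| 47/54 | 87.0%, pass | k ≤ 1 | 70.4 points |
| 48/54 | 88.9%, pass | k = 0 | 88.9 points |

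At 42 or fewer both results fail (42 + 6 = 48). At 49 or more both pass. The last three rows need gaps too large to be likely.

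**Other counts**
- w = 3 (57 stayers): only 46, 47 or 48 favourable can change, with k ≤ 2, k ≤ 1 and k = 0 (gaps 14.0, 49.1 and 84.2 points). 49/57 cannot change.
- w = 12 (48 stayers): 41/48 = 85.4% is reported as a pass, but with 6 of 12 withdrawers favourable the full result is 47/60 = 78.3%. In reverse, 38/48 = 79.2% is reported as a fail, but with 11 of 12 favourable it is 49/60 = 81.7%.

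**Pooled reading.** If the criterion pools 60 AYA and 10 health care providers, 56/70 = 80.0% fails and 57/70 is needed. Six AYA withdrawals then shift the result by 6/70 × 15 = 1.3 points or 6/70 × 35 = 3.0 points.

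**Likelihood items (0 to 10).** Six withdrawals and a 2-point mean difference shift the mean by 6/60 × 2 = 0.2.

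**The case against.** The strongest reply is that the final data analysis is not defined in Section 13. Usability is a separate, separately paid step that is finished before the 3-month phase, so a team could reasonably report it for all raters and apply the exclusion only to the 3-month outcomes. That would be a sensible practice, but the plan does not say so, and its literal wording says the opposite.

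Second, few people may be exposed. Someone who rates the tool and declines the 3-month phase is recorded as declining, not as withdrawn, and missing the final visit is not called withdrawal either. Those at risk are essentially the participants who continue, a number the documents do not give. If 30 continued (an illustration only), 12 withdrawals would be 40% of them. This stands. It limits the size of the problem and makes the w = 12 case an extreme one.

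Third, little depends on the result: the WAMMI is listed as exploratory, the data are called descriptive, and no go/no-go decision is attached to the 80% mark. This also stands and keeps the point minor. Even so, Section 4 places usability in the primary endpoint, and a descriptive percentage still needs the right denominator.

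Fourth, excluding withdrawers' data could be a deliberate protection in a study that enrols minors, some possibly under a parental-permission waiver. The documents do not give this reason, but consent does limit what can be recovered.

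**Conclusion.** The concern holds, as a minor point. Followed as written, Section 13 removes finished usability and likelihood ratings from the analysis when a participant later withdraws, and no other section keeps them. Confidence in that reading of the wording is high.

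The effect on results is unknown in size and direction. Under the assumed 6 withdrawals among 60 AYA raters it is 1.5 to 3.5 points for gaps of 15 to 35 points, and it matters for the >80% result only close to the threshold. It is zero if withdrawers rate the tool as others do.

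Two matters are wording only. The exclusion probably covers people withdrawn by the study, but Section 13 does not say so. Read literally, the rule also sits awkwardly with completion/dropout as an outcome, although Section 17 already counts drop-outs and retention for monitoring.

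**What to change.** Replace the Section 13 sentence with wording such as: *No new data are collected after withdrawal; data collected before withdrawal are kept and analysed, where consent allows, unless the participant asks for their removal.*

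In the Phase 3 analysis text of Section 5:
- Define the usability set as everyone who completed the baseline #HerHeart WAMMI.
- Limit exclusion to outcomes that need 3-month data.
- Count withdrawers in the completion/dropout denominator, among those who entered the 3-month phase and, separately, among all enrolled in Phase 3.
- State whether participants withdrawn by the study, those who decline the 3-month phase, and those who miss the final visit count as withdrawn.

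A table comparing completers with non-completers is optional.

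The cost is one protocol sentence, a short analysis-set definition, and matching wording in the consent, assent and parental-permission forms, which are not among the documents reviewed. If signed forms promised exclusion after withdrawal, data from people already consented may not be usable. The sponsor should also accept that reported usability may come out less favourable than under the current rule, although it could equally come out higher.

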- Patient at CHOA Hughes Spalding Adolescent Medicine Practice or the Grady Health System Teen Program
- Age 13-21 years
- Self-identifying as non-Hispanic Black or White race (inclusive of Hispanic ethnicity)
- Self-identifying as female
- Visit type is annual wellness/health check, behavioral/mental health, or reproductive/gynecological health
- Consistent access to a mobile device with internet capability

Exclusion Criteria (AYAs):

- Cognitive impairment limiting ability to complete study procedure
- Spoken and written language other than English

- Diagnosis of hypertension, diabetes, or hyperlipidemia requiring medications, or atherosclerotic cardiovascular disease
- Past or current diagnosis of a DSM-V eating disorder
- Diagnosis of schizophrenia, bipolar disorder, or psychiatric hospitalization in the past 12 months
- Pregnant at the time of the study.

Inclusion Criteria (HCPs):

- Clinical team member (physician or nurse practitioner, nurse, social worker, psychologist, health educator, medical assistant, dietitian) at the CHOA Hughes Spalding Adolescent Medicine Practice or the Grady Health System Teen Program
- Practicing at one of the study sites at least twice per month on average over the past year

Exclusion Criteria (HCPs)

- Member of the research study team

10. Vulnerable Populations

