The proposed study involves the vulnerable population of children under the legal age of consent to procedures involved in the research. Though the research involves no more than minimal risk, we will take safeguards to protect the rights and welfare of these individuals. Written parental permission will be obtained for all individuals under the age of 18 years if the parent or legal guardian is present at the time of recruitment. Permission of one parent is sufficient even if the other parent is alive, known, competent, reasonably available, and shares legal responsibility for the care and custody of the child. Only parents or legal guardians listed in the child's medical record will be able to provide permission. We will request a Waiver of Parental Permission as permitted under permitted under 45 CFR 46.408(c) for those patients under 18 years of age who present alone for a visit for reproductive health visits. Adolescents have the legal right to seek care for certain sexual health services, including contraception and sexually transmitted infection testing and treatment, in the state of Georgia. To contact the parent or guardian for consent to participate in research would violate the adolescents' legal right to privacy by disclosing their presence at the clinical practice, even though the study does not discuss sexual health.

Additionally, we will obtain written assent from all children to ensure they understand the study and agree to participate. In the event a child's parent or guardian is not present, we will obtain written consent from the child using a consent form that provides adequate study information for the subject to make an informed decision. For patients 18 years or older, we will discuss how the study will use and disclose individually identifiable health information and obtain written consent. Because participants may receive clinical care from the PI or Co-I, who are providers at the CHOA Adolescent Medicine practice and the Grady Teen Health Program, the consent and assent process will be carried out by the research coordinator. This will aid in minimizing coercion or undue influence by the PI.

11. Local Number of Participants

We will recruit 90 AYA subjects and 10 HCP subjects. Participants will be recruited from the CHOA Adolescent Medicine Practice and the Grady Health System Teen Program.

12. Recruitment Methods

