For aims 1 and 3, the research coordinator will preliminarily screen AYA patients from the CHOA Adolescent Medicine Practice and the Grady Teen Health Program using the Epic Electronic Medical Record system. Patients who meet preliminary eligibility criteria (race, gender, age) will be added to the screening log (Screening Log.xlsx) and contacted via phone by the research assistant to see if they are interested in participating in the study when they come in for their clinical visit. For aim 2, participants will be recruited from the Emory Pipeline Collaborative (EPiC).

- Participants will be recruited both in-person and virtually, due to current COVID-19 public health recommendations.
- Patients reached via phone will be provided a brief overview of the study and the research coordinator will administer the screening eligibility questionnaire (Screening Survey.docx).
- Those who are eligible and interested in participating will be asked if they prefer to attend a study visit either an hour before or an hour after their clinical visit. Participants will also have the option to book a separate study visit at a time not related to their clinical visit, to occur via Zoom.
- Patients reached via phone who are not interested in participating will be noted as such on the screening log.
- Patients who are not reached via phone using the screening criteria but eligible for the study may still be approached at the time of their clinical visit.
- For patients attending the clinic in person, the research coordinator will approach eligible AYAs in the waiting room of the clinics and lead them to a private sitting area in order to provide a brief overview of the study and administer the screening eligibility questionnaire (Screening Survey.docx).
- For patients attending the clinic via telemedicne, the physician conducting the visit will ask the patient if they are interested in learning about the study. If so, the research coordinator will schedule a date and time with the patient to provide a brief overview of the study and administer the screening eligibility questionnaire via a password-protected Zoom videoconference.

If ineligible, participants will be informed that they are not eligible to participate in the study. If eligible, AYA participants will then carry out the consent and study procedures for each study phase as described in Section 21 and 6, respectively. Interested participants will the carry out

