Prospective participants who have not attained the legal age for consent (e.g. individuals under the age of 18 years), as determined by the age in their medical record, will be required to give written assent. Written parental permission will also be obtained for these individuals if the parent or guardian is present. Parental permission will be obtained from one parent, even if the other parent is alive, known, competent, reasonably available, and shares legal responsibility for the care and custody of the child. Only parents or legal guardians listed in the child's medical record will be able to provide permission. If the parent or guardian is not present, we will not contact them for the sole purpose of informed consent as doing so may violate the adolescents' right to private healthcare for certain sexual health services. We will instead present the participant with a consent form that provides enough information for the subject to make an informed decision. Given this study includes no more than minimal risk, we have applied for a Waiver of Parental Permission as permitted under permitted under 45 CFR 46.408(c) for those patients under 18 years of age who present alone for a visit for reproductive health visits.

21. Setting

Participants will be recruited from the CHOA Hughes Spalding Adolescent Medicine Practice and the Grady Health Teen Clinic Program. For patients visiting the clinics in person, recruitment procedures will take place either before the visit using the screening and recruitment phone call or in the waiting rooms of each clinic, while consent/assent and study procedures will take place in a private office. For patients visiting the clinics virtually (telemedicine) recruitment, consent, and study procedures will take place via Zoom videoconferencing (password-protected). Participants who agree to participate in the intervention in Aim 3 will attend a study visit at the Emory Children's Center Research Unit.

A CHOA community advisory board will be made available to us. The advisory board consists of local business, community and nonprofit leaders who are not only dedicated to community service, but also focused on the needs and well-being of children in their communities. Board members work as advocates and liaisons between the community and Children's.

22. Resources Available

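### The rule letting an unaccompanied minor sign alone has no visit-type limit, while the requested parental-permission waiver covers reproductive health visits only, so some 13-17-year-olds could be enrolled with neither.

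*Combined protocol and SAP*

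**What the plan says.** **Who is eligible.** Section 9 (Subject Population) sets the age criterion at "Age 13-21 years", so minors of 13 to 17 are included. It admits three kinds of visit: "Visit type is annual wellness/health check, behavioral/mental health, or reproductive/gynecological health". Section 22 confirms that the CHOA practice sees all three kinds.

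**When a parent's permission is sought.** Section 10 (Vulnerable Populations) ties it to attendance: "Written parental permission will be obtained for all individuals under the age of 18 years if the parent or legal guardian is present" when the patient is recruited.

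**What happens when no parent is there.** Section 10: "In the event a child's parent or guardian is not present, we will obtain written consent from the child using a consent form". The subsection of Section 20 (Consent Process) on participants who are not yet adults agrees: "If the parent or guardian is not present, we will not contact them for the sole purpose of informed consent". That sentence goes on to explain that contact might breach the adolescent's right to private care for certain sexual health services. The next sentence gives the participant a consent form of her own.

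**What the waiver covers.** Both sections describe a waiver under 45 CFR 46.408(c) "for those patients under 18 years of age who present alone for a visit for reproductive health visits". Section 10 says it will be requested; Section 20 says it has been applied for.

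**A second test.** The opening paragraph of Section 20 invokes the waiver only when two conditions are met: the parent is not in clinic, and contacting the parent would breach the adolescent's privacy about certain sexual health services.

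**The concern.** The route by which a minor consents alone is wider than the waiver meant to support it. The route depends on one fact, that the parent is absent. The waiver depends on two, that the minor is alone and that the visit is for reproductive health. A coordinator who follows Section 10, or the minors' subsection of Section 20, would have an unaccompanied 15-year-old at a wellness or counselling visit sign for herself, and nothing in the plan supplies either permission or a waiver for her.

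The protocol itself treats minors as a vulnerable population and presents parental permission as a safeguard. It justifies setting that safeguard aside by the need to keep a sexual-health visit confidential. It does not argue that the same need arises at the other two visit types. What is at stake is the protection of these participants and the clarity of the instruction staff will follow.

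**Working it through.** The plan gives no figure on this point, so there is nothing to recompute. The check sets the rules side by side for one case: a patient aged 13 to 17 whose parent is not present.

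| Eligible visit type (Section 9) | Section 10 and minors' subsection of Section 20 | Opening paragraph of Section 20 | Waiver as requested (Sections 10 and 20) |
|---|---|---|---|
| Reproductive/gynecological | Parent not contacted; minor signs alone | Waiver invoked if contact would breach sexual-health privacy | Covered |
| Annual wellness | Parent not contacted; minor signs alone | No rule stated where that privacy ground is absent | Not covered |
| Behavioral/mental health | Parent not contacted; minor signs alone | No rule stated where that privacy ground is absent | Not covered |

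1. *Is the child-alone rule limited by visit type?* No. Neither the Section 10 sentence nor the Section 20 sentence names a visit type. The sexual-health clause in Section 20 gives the reason for the rule; it does not state a condition for applying it.

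2. *Is the waiver limited by visit type?* Yes. Both sections name reproductive health visits and no others.

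3. *Does another provision close the gap?* None was found. The plan does not exclude unaccompanied minors at wellness or mental health visits, does not defer their enrolment until a parent can be reached, and gives no other route to permission.

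4. *Does the opening of Section 20 settle it?* No. Its privacy test is a real condition, so it is narrower than the rule later in the same section, and the two conflict. If the opening paragraph governs, the waiver is not invoked for a minor whose visit raises no sexual-health privacy issue, and the plan does not say what to do with her.

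Visit types outside the waiver: 3 eligible − 1 covered = 2. This counts categories, not participants.

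**The case against.** The best defence is to read the passages as a whole. In Section 20 the no-contact sentence carries its sexual-health reason within it and leads straight to the reproductive-health waiver. In Section 10 the child-alone sentence follows the waiver and its rationale. On this reading the authors were describing a single confidential-care pathway, and the opening paragraph of Section 20 shows what they meant. An unaccompanied minor at a wellness visit is then simply not addressed, and silence is not an instruction to enrol her.

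This may well be what was intended, and it is why the point is that such minors could be enrolled, not that they would be. It does not remove the problem. The rule as written is general, the condition appears in only one of the three places, and even the narrower reading leaves two eligible visit types without a rule.

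Several stronger conclusions are tempting, and the documents do not support them:

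- *A count of affected participants among the 60 in Phase 3.* This would need the share who are minors, alone, and at a non-reproductive visit. The documents give none of these. Eligibility runs to 21, and one of the two sites is a family planning program (Section 22), so the share could be small.
- *That separate Zoom study visits fall outside the waiver.* The waiver turns on how the minor presented for the clinical visit, not on where the study visit takes place. Its application to a stand-alone Zoom visit is not spelled out.
- *That the pre-visit telephone call defeats the privacy rationale.* Section 12 has patients "contacted via phone by the research assistant to see if they are interested in participating", but whose number is on file is not stated.
- *That data would have to be removed.* The documents state no such consequence, and the IRB's decision on the waiver, including its scope, cannot be seen.

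**Conclusion.** The point holds as an internal contradiction in the consent rules. Sections 10 and 20 allow a minor to consent alone whenever the parent is absent; the waiver in the same sections reaches only one of the three eligible visit types; and the opening of Section 20 applies a different test. Following the general rule could enrol 13-17-year-olds at wellness or behavioral/mental health visits with neither parental permission nor a waiver.

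The size in participants is unknown. The conclusion rests on the text alone and on two assumptions: that some minors attend these visits unaccompanied, and that the waiver granted, if any, is no wider than the one described. If the IRB in fact approved a wider waiver, the protocol text would still need correcting to match it. The change should be made because it concerns the protection of minors and is cheap.

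**What to change.** Reconcile Section 10, the opening of Section 20 and the minors' subsection of Section 20 so that the child-alone route and the waiver cover the same visits. There are two ways to do this:

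- Limit the child-alone route to visits the waiver covers, and state that an unaccompanied minor at any other visit type is enrolled only with parental permission. That permission could be obtained in person or through the Zoom consent process that Section 20 already plans for telemedicine patients and their parents.
- Obtain an IRB waiver that expressly covers wellness and behavioral/mental health visits, with its own justification, before using the child-alone route there.

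Under either option, use one test with the same wording in all three places, and replace the language about requesting or applying for the waiver with its actual status and scope.

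The cost is revised wording and an IRB amendment. Under the first option, recruitment of minors who attend alone would be slightly slower.
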